## 5. TREATMENT PLAN

### 5.1 STUDY PROCEDURES

**Screening (maximum 21 days):** The screening period begins once the informed consent is signed.

- Informed Consent
- Demographics
- Medical History
- Concomitant Medications
- Physical Exam
- Vital Signs (blood pressure, pulse, oxygen saturation, respiratory rate and body temperature)
- Height
- Weight
- Body Mass Index (BMI) [BMI= weight (kg)/height (m^2)]
- Blood Draw:
  - Chemistry panel: Albumin, Alkaline Phosphatase, ALT, AST, GGT, Bicarbonate (CO2), Calcium, Chloride, Creatinine, Glucose, Potassium, Sodium, Total Bilirubin, Total Protein, Urea Nitrogen
  - Hematology Panel: Complete Blood Count (CBC) with differential and platelets
  - Infectious disease screening: HIV antibody, Hepatitis C antibody, Hepatitis B panel (HBsAg, anti-HBc, anti-HBs), and interferon gamma release assay (IGRA)
  - Serum pregnancy test for WOCBP
  - Inflammation Markers: CRP (C-Reactive Protein), ESR (Erythrocyte Sedimentation Rate)

Visit 1 (day 0, must occur within 21 days of signing informed consent):

- ***At least 45 minutes before injection:*** Remove syringe from refrigeration and lay flat; allow to warm to room temperature. Do not heat
- Pre-injection
  - Physical Exam
  - DLQI

- Urine pregnancy
- HISCR
- PGA
- Disease Activity Score
- Modified Sartorius
- HADS
- VAS for disease
- VAS for pain
- Vital signs (blood pressure, pulse, oxygen saturation, respiratory rate and body temperature)
- Blood draw for PK and biomarker analysis
- Bermekimab subcutaneous injection, in accordance with injection site determined by BMI at Screening
- 1 hour monitoring for injection reaction
- Vital signs (blood pressure, pulse, oxygen saturation, respiratory rate and body temperature) one hour post injection (70 +/- 10 minutes)
- Adverse event monitoring
- Concomitant medications/treatments

Visit 2 (day 7 +/-2):

- ***At least 45 minutes before injection:*** Remove syringe from refrigeration and lay flat; allow to warm to room temperature. Do not heat
- Pre-injection
  - Urine pregnancy
  - Vital signs (blood pressure, pulse, oxygen saturation, respiratory rate and body temperature)
- Bermekimab subcutaneous injection, in accordance with injection site determined by BMI at Screening
- 1 hour monitoring for injection reaction
- Vital signs (blood pressure, pulse, oxygen saturation, respiratory rate and body temperature) one hour post injection (70 +/- 10 minutes)
- Adverse event monitoring
- Concomitant medications/treatments

## Visit 3 (day 14 +/-2):

- ***At least 45 minutes before injection:*** Remove syringe from refrigeration and lay flat; allow to warm to room temperature. Do not heat
- Pre-injection
  - Physical Exam
  - DLQI
  - Urine pregnancy
  - HISCR
  - PGA
  - Disease Activity Score
  - Modified Sartorius
  - HADS
  - VAS for disease
  - VAS for pain
  - Vital signs (blood pressure, pulse, oxygen saturation, respiratory rate and body temperature)
  - Blood draw for chemistry, hematology, CRP, ESR and blood draw for PK and biomarker analysis
- Bermekimab subcutaneous injection, in accordance with injection site determined by BMI at Screening
- 1 hour monitoring for injection reaction
- Vital signs (blood pressure, pulse, oxygen saturation, respiratory rate and body temperature) one hour post injection (70 +/- 10 minutes)
- Adverse event monitoring
- Concomitant medications/treatments

## Visit 4 (day 21 +/-2):

- ***At least 45 minutes before injection:*** Remove syringe from refrigeration and lay flat; allow to warm to room temperature. Do not heat
- Pre-injection
  - Urine pregnancy
  - Vital signs (blood pressure, pulse, oxygen saturation, respiratory rate and body temperature)

- Bermekimab subcutaneous injection, in accordance with injection site determined by BMI at Screening
- 1 hour monitoring for injection reaction
- Vital signs (blood pressure, pulse, oxygen saturation, respiratory rate and body temperature) one hour post injection (70 +/- 10 minutes)
- Adverse event monitoring
- Concomitant medications/treatments

Visit 5 (day 28 +/-2):

- ***At least 45 minutes before injection:*** Remove syringe from refrigeration and lay flat; allow to warm to room temperature. Do not heat
- Pre-injection
  - Physical Exam
  - DLQI
  - Urine pregnancy
  - HISCR
  - PGA
  - Disease Activity Score
  - Modified Sartorius
  - HADS
  - VAS for disease
  - VAS for pain
  - Blood draw for chemistry, hematology, CRP, ESR and blood draw for PK and biomarker analysis
  - Vital signs (blood pressure, pulse, oxygen saturation, respiratory rate and body temperature)
- Bermekimab subcutaneous injection, in accordance with injection site determined by BMI at Screening
- 1 hour monitoring for injection reaction
- Vital signs (blood pressure, pulse, oxygen saturation, respiratory rate and body temperature) one hour post injection (70 +/- 10 minutes)
- Adverse event monitoring
- Concomitant medications/treatments

## Visit 6 (day 35 +/-2):

- ***At least 45 minutes before injection:*** Remove syringe from refrigeration and lay flat; allow to warm to room temperature. Do not heat
- Pre-injection
  - Urine pregnancy
  - Vital signs (blood pressure, pulse, oxygen saturation, respiratory rate and body temperature)
- Bermekimab subcutaneous injection, in accordance with injection site determined by BMI at Screening
- 1 hour monitoring for injection reaction
- Vital signs (blood pressure, pulse, oxygen saturation, respiratory rate and body temperature) one hour post injection (70 +/- 10 minutes)
- Adverse event monitoring
- Concomitant medications/treatments

## Visit 7 (day 42 +/-2):

- ***At least 45 minutes before injection:*** Remove syringe from refrigeration and lay flat; allow to warm to room temperature. Do not heat
- Pre-injection
  - Physical Exam
  - DLQI
  - Urine pregnancy
  - HISCR
  - PGA
  - Disease Activity Score
  - Modified Sartorius
  - HADS
  - VAS for disease
  - VAS for pain
  - Vital signs (blood pressure, pulse, oxygen saturation, respiratory rate and body temperature)

- Bermekimab subcutaneous injection, in accordance with injection site determined by BMI at Screening
- 1 hour monitoring for injection reaction
- Vital signs (blood pressure, pulse, oxygen saturation, respiratory rate and body temperature) one hour post injection (70 +/- 10 minutes)
- Adverse event monitoring
- Concomitant medications/treatments

Visit 8 (day 49 +/-2):

- ***At least 45 minutes before injection:*** Remove syringe from refrigeration and lay flat; allow to warm to room temperature. Do not heat
- Pre-injection
  - Urine pregnancy
  - Vital signs (blood pressure, pulse, oxygen saturation, respiratory rate and body temperature)
- Bermekimab subcutaneous injection, in accordance with injection site determined by BMI at Screening
- 1 hour monitoring for injection reaction
- Vital signs (blood pressure, pulse, oxygen saturation, respiratory rate and body temperature) one hour post injection (70 +/- 10 minutes)
- Adverse event monitoring
- Concomitant medications/treatments

Visit 9 (day 56 +/-2):

- ***At least 45 minutes before injection:*** Remove syringe from refrigeration and lay flat; allow to warm to room temperature. Do not heat
- Pre-injection
  - Physical Exam
  - DLQI
  - Urine pregnancy
  - HISCR
  - PGA
  - Disease Activity Score
  - Modified Sartorius

- HADS
- VAS for disease
- VAS for pain
- Blood draw for chemistry, hematology, CRP, ESR and blood draw for PK and biomarker analysis
- Vital signs (blood pressure, pulse, oxygen saturation, respiratory rate and body temperature)
- Bermekimab subcutaneous injection, in accordance with injection site determined by BMI at Screening
- 1 hour monitoring for injection reaction
- Vital signs (blood pressure, pulse, oxygen saturation, respiratory rate and body temperature) one hour post injection (70 +/- 10 minutes)
- Adverse event monitoring
- Concomitant medications/treatments

Visit 10 (day 63 +/-2):

- ***At least 45 minutes before injection:*** Remove syringe from refrigeration and lay flat; allow to warm to room temperature. Do not heat
- Pre-injection
  - Urine pregnancy
  - Vital signs (blood pressure, pulse, oxygen saturation, respiratory rate and body temperature)
- Bermekimab subcutaneous injection, in accordance with injection site determined by BMI at Screening
- 1 hour monitoring for injection reaction
- Vital signs (blood pressure, pulse, oxygen saturation, respiratory rate and body temperature) one hour post injection (70 +/- 10 minutes)
- Adverse event monitoring
- Concomitant medications/treatments

Visit 11 (day 70 +/-2):

- ***At least 45 minutes before injection:*** Remove syringe from refrigeration and lay flat; allow to warm to room temperature. Do not heat
- Pre-injection

- Physical Exam
- DLQI
- Urine pregnancy
- HISCR
- PGA
- Disease Activity Score
- Modified Sartorius
- HADS
- VAS for disease
- VAS for pain
- Vital signs (blood pressure, pulse, oxygen saturation, respiratory rate and body temperature)
- Bermekimab subcutaneous injection, in accordance with injection site determined by BMI at Screening
- 1 hour monitoring for injection reaction
- Vital signs (blood pressure, pulse, oxygen saturation, respiratory rate and body temperature) one hour post injection (70 +/- 10 minutes)
- Adverse event monitoring
- Concomitant medications/treatments

Visit 12 (day 77 +/-2):

- ***At least 45 minutes before injection:*** Remove syringe from refrigeration and lay flat; allow to warm to room temperature. Do not heat
- Pre-injection
  - Urine pregnancy
  - Vital signs (blood pressure, pulse, oxygen saturation, respiratory rate and body temperature)
- Bermekimab subcutaneous injection, in accordance with injection site determined by BMI at Screening
- 1 hour monitoring for injection reaction
- Vital signs (blood pressure, pulse, oxygen saturation, respiratory rate and body temperature) one hour post injection (70 +/- 10 minutes)
- Adverse event monitoring
- Concomitant medications/treatments

## Visit 13 (day 84 +/-2):

- ***At least 45 minutes before injection:*** Remove syringe from refrigeration and lay flat; allow to warm to room temperature. Do not heat
- Pre Injection
  - Physical Exam
  - DLQI
  - Urine pregnancy
  - HISCR
  - PGA
  - Disease Activity Score
  - Modified Sartorius
  - HADS
  - VAS for disease
  - VAS for pain
  - Blood draw for chemistry, hematology, CRP, ESR and blood draw for PK and biomarker analysis
  - Vital signs (blood pressure, pulse, oxygen saturation, respiratory rate and body temperature)
- Bermekimab subcutaneous injection, in accordance with injection site determined by BMI at Screening
- 1 hour monitoring for injection reactions
- Vital signs (blood pressure, pulse, oxygen saturation, respiratory rate and body temperature) one hour post injection (70 +/- 10 minutes)
- Adverse event monitoring
- Concomitant medications/treatments

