An investigator initiated phase II RCT trial among patients not eligible for adalimumab (EudraCT number 2015-002321-20; ClinicalTrials.gov NCT02643654) was recently completed and showed promising results for activity of bermekimab in HS. Twenty patients with severe HS and with either primary or secondary failure of previous antiTNF agents, or who were unwilling to receive subcutaneous adalimumab treatment, were randomly allocated (1:1) to receive, in a blinded fashion, every other week treatment with placebo or bermekimab at a dose of 7.5 mg/kg IV. Treatment was administered intravenously for 12 weeks. The primary efficacy endpoint was the positive HiSCR score, that was achieved among 10% of patients allocated to placebo and 60% of patients allocated to bermekimab. The odds ratio for positive HiSCR after 12 weeks of treatment was 13.50 (95% confidence intervals 1.19-152.51, p: 0.035). Analysis of the secondary endpoints showed some remarkable advantages of bermekimab treatment versus placebo treatment: a) blind follow-up for 12 weeks after stopping treatment showed that clinical efficacy was sustained, in that a positive HiSCR score was found in 40% of the treatment group and 0% of patients receiving placebo (p: 0.043); b) positive patient reported outcomes were found at week 12 in 70% and 30% respectively (p: 0.010); c) the median time to new HS flare-up was prolonged to 11 weeks and 7 weeks respectively; d) with the use of dermal ultrasound at week 12, a 20% or more decrease in total depth of involved skin lesions was found in 77.8% and 22.2%, respectively (p: 0.029); and e) serum IL-8 was decreased at week 12 in 90% and 40% respectively (p: 0.029).

In previous dermatology studies bermekimab was well tolerated and showed impressive therapeutic activity. Dose ranging for the subcutaneous formulation of bermekimab is now being studied in a 12 week open label treatment regimen for HS in order to establish the basis for further randomized studies using subcutaneous administration.

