## 7. ASSESSMENT OF SAFETY

Safety will be assessed by monitoring adverse events, vital signs, physical examinations, and clinical laboratory measurements. All subjects will be included in the safety analysis. Adverse events will be monitored from visit 1 (post-injection) through visit 14. Any serious adverse events or grade 2 or greater probably or definitely related events will be followed up until resolution.

Study drug will be administered under close observation in a facility equipped to handle anaphylaxis. Subjects must be closely monitored until at least 1 hour following the administration of the antibody or 1 hour after their vital signs have stabilized.

Any AE (with the exception of worsening HS symptoms or injection site reactions) of grade 2 or higher must be reported to the sponsor within 24 hours of learning of the event. Any grade 3 or greater injection site reaction must be reported to the sponsor within 24 hours of learning of the event.

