## 8.2 Study Endpoints

The primary endpoint of this study is the safety and tolerability of bermekimab at 400 mg weekly subcutaneous dose.

The secondary endpoints include:

- Hidradenitis Suppurativa Clinical Response (HiSCR) score (baseline to visit 13). For this score patients are defined as achievers or non-achievers. The positive HiSCR score is defined as a  $\geq 50\%$  reduction in inflammatory lesion AN count (sum of abscesses and inflammatory nodules), and no increase in abscesses or draining fistulas in HS compared with the lesions counted on visit 1. The HiSCR score, including inflammatory lesion count, will be measured on visits 1, 3, 5, 7, 9, 11, 13 and 14.
- Pharmacokinetics (PK) (baseline to visit 13). An enzyme-linked immunosorbent assay (ELISA) has been developed to specifically measure bermekimab levels in human plasma. Blood will be drawn into a single 6 ml collection tube at each PK collection time point (sample collection is pre-dose at visit 1, visit 3, visit 5, visit 9 and visit 13). These samples will be collected per the study lab manual and immediately shipped to the Sponsor for PK analysis. The PK samples will also be used to test for the presence of antibodies against bermekimab.
- Physician's Global Assessment (PGA) (baseline to visit 13). This is defined as: a) clear when the total number of abscesses is 0, the total number of draining fistulas is 0, the total number of inflammatory nodules is 0 and the total number of non-inflammatory nodules is 0; b) minimal when the total number of abscesses is 0, the total number of draining fistulas is 0, the total number of inflammatory nodules is 0 and there is presence of non-inflammatory nodules; c) mild when the total number of abscesses is 0, the total number of draining fistulas is 0, and the total number of inflammatory nodules is 1-4, or when there is presence of one abscess or draining fistula and absence of any inflammatory nodules; d) moderate when the total number of abscesses is 0, the total number of draining fistulas is 0 and the total number of inflammatory nodules is at least 5; or when there is presence of one abscess or draining fistula and at least one inflammatory nodule; or when there are 2-5 abscesses or draining fistulas and fewer than 10 inflammatory nodules; e) severe when the total number of abscesses or draining fistulas is 2-5 and the total number of inflammatory nodules is at least 10; and f) very severe when there

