## **9.2 DEFINITION OF SERIOUS ADVERSE EVENT (SAE)**

A serious adverse event is defined as any untoward medical occurrence that meets any of the following criteria:

- Results in death;
- Life-threatening;
- Requires or prolongs inpatient hospitalization;
- Results in a persistent or significant disability;
- An important medical event that, while it may not result in death or be immediately life-threatening or require/prolong hospitalization, may jeopardize the subject and/or may require medical or surgical intervention to prevent one of the outcomes listed above. Examples of such events are intensive treatment in an emergency room or at home for allergic bronchospasm; blood dyscrasias or convulsions that do not result in hospitalization.

Note that seriousness and severity should not be confused. A subject could experience a severe headache that would not qualify as an SAE, while another might experience a mild stroke that, while not severe, would be considered serious.

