### **10.1 Statistical Hypothesis**

No formal hypothesis tests will be performed for the primary endpoints.

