### **10.2 Determination of Sample Size**

The sample size chosen was one of convenience, and no formal sample size calculations were performed.

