## 10.5.2 Safety Analysis

The primary objective of this study is to evaluate the safety and tolerability of 400mg dose of bermekimab. Safety endpoints will be evaluated by monitoring adverse events from clinical and laboratory reporting. The safety analysis will be based on the SAF population defined as all subject who received at least one dose of study medication. A summary of safety results will be presented for each treatment group.

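### No scheduled laboratory value follows the thirteenth injection, Section 9 does not require pregnancies to be reported or followed to outcome, and the 7-day capture window after the last dose is not justified.

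*Combined protocol and SAP*

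**What the plan says.** Section 8.2 states: "The primary endpoint of this study is the safety and tolerability of bermekimab at 400 mg weekly subcutaneous dose". Section 10.5.2 repeats it as the objective and bases the evaluation on clinical and laboratory reporting. Section 10.5.2.2 then summarizes every laboratory result, its change from baseline, and the laboratory events of grade 2 or higher.

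The schedule in 5.1 puts the final chemistry and hematology at visit 13 (day 84), among the procedures done before that visit's injection: "Blood draw for chemistry, hematology, CRP, ESR and blood draw for PK and biomarker analysis". Visit 14 (day 91) has a physical exam, disease scores, vital signs, adverse events and concomitant medications, but no blood draw. The lab row of the 5.2 calendar also ends at visit 13.

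On events, Section 7 says: "Adverse events will be monitored from visit 1 (post-injection) through visit 14". Section 9.3 uses visit 14, or seven days after the last dose for patients who leave early. Section 10.5.2.1 ends treatment-emergent events at the last study visit.

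Pregnancy is an exclusion criterion, is tested at screening and at every injection visit, and is a reason to stop therapy in 5.3. Section 9.2 opens "A serious adverse event is defined as any untoward medical occurrence that meets any of the following criteria" and lists death, threat to life, hospitalization, disability and important medical events. Neither 9.2 nor the reporting rules in 9.6 mention pregnancy or a child.

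**The concern.** The trial is meant to describe the safety of a course of 13 weekly 400 mg injections. Three parts of that description are not collected by a patient and site who follow the plan exactly.

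- **Laboratory values after the full course.** The last draw reflects at most 12 injections.
- **Outcomes of exposed pregnancies.** A pregnancy found at an injection visit after visit 1 has already been exposed. Any outcome at term falls after visit 14, so it is known only if the protocol asks for it.
- **New events after visit 14.** No period of observation off treatment is planned, so the data cannot support a statement about events that begin after that point.

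With 20 patients and no control group, each missing observation is a visible share of the evidence. Section 1.2 says the study is to establish the basis for further randomized studies, so gaps here carry forward.

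**Working it through.** No power or sample-size calculation applies, so the check is calendar arithmetic and a comparison of sections.

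**1. The plan's own duration.** The synopsis gives about 16 weeks: 3 of screening and 13 of treatment. Screening is at most 21 days, 21/7 = 3. Day 0 to visit 14 (day 91) is 91/7 = 13. Total 16, so the figure reproduces. Visit 14 therefore closes the treatment period and there is no separate follow-up. The exposure formula in 10.5.5 agrees: (84 − 0) + 7 = 91 days, so the week after the last injection counts as exposure.

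**2. Injections followed by a scheduled lab.** Thirteen weekly injections fall on days 0, 7, …, 84. Labs after screening are at visits 3, 5, 9 and 13 in 5.1, and at visits 2, 4, 9 and 13 in the calendar. The two differ early but share the last draw. Taken before injection 13, it follows injections 1 to 12. Result: 12 of 13 covered, and 0 draws after the thirteenth.

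**3. What existing follow-up covers.** Section 9.1 makes a clinically significant laboratory abnormality an adverse event. Section 7 follows serious events, and grade 2 or higher events judged probably or definitely related, until resolution. Section 9.6 follows serious events to stabilization. That leaves non-serious abnormalities that are grade 1, or of any grade but judged only possibly related or less on the 9.5 scale. For these, no repeat test is scheduled after visit 13.

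**4. Window for new events after the last injection.** Nominal: 91 − 84 = 7 days. With ±2 days on each visit, the shortest is 89 − 86 = 3 and the longest 93 − 82 = 11.

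**5. Is 7 days short?** The documents give no half-life and no reason for the window. As an assumption only, take a half-life h of 7, 14, 21 or 28 days with simple exponential decline. The fraction of drug left 7 days later is 0.5^(7/h):

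| Assumed h (days) | Left after 7 days |
|---|---|
| 7 | 50% |
| 14 | 71% |
| 21 | 79% |
| 28 | 84% |

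Across this range visit 14 is still an on-drug visit. This shows why a rationale is needed; it does not set a required window.

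**6. Pregnancy.** Set side by side, 4.1 requires contraception for the study period, 5.1 tests repeatedly, and 5.3 stops therapy. Section 9 then has no instruction to report the pregnancy, none to collect its outcome, and no serious-event criterion that names a congenital anomaly.

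**The case against.** The best defence is that this is a small descriptive study: "No formal hypothesis tests will be performed for the primary endpoints", and "no formal sample size calculations were performed". Labs follow 12 of 13 identical weekly doses, visit 14 still has an exam, vital signs and event monitoring, and serious or clearly related events are pursued to resolution. This stands as a limit on severity. It does not supply the missing values, and the follow-up rules act only on events already recorded.

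Some stronger readings are tempting, and the documents do not support them.

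- **That safety capture should last 12 weeks.** Section 1.2 reports of an earlier trial that "blind follow-up for 12 weeks after stopping treatment showed that clinical efficacy was sustained", and a reader might set 7 days against those 84. But that is sustained lesion response after intravenous dosing every other week, with 10 patients per arm. It measures neither drug persistence nor late toxicity, so the ratio compares unlike quantities.
- **That no delayed effect could be seen.** Events are monitored from day 0 to day 91, so a late effect of the first doses has up to 13 weeks to appear. What is lost is onset after visit 14.
- **That two injections follow the last lab.** The calendar marks an injection and a PK draw at visit 14. This conflicts with the 13 injections in the synopsis, with visit 14 in 5.1, and with the visit 13 PK sample in 6.1. The table was machine-read. The conflict must be reconciled, but it does not measure this gap.
- **That the draw should simply move to visit 14.** The interval after visit 9 would grow from 84 − 56 = 28 to 91 − 56 = 35 days. A patient who took dose 13 and missed visit 14 would have five doses (9 to 13) with no later lab, against one now.

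On pregnancy, consent pages are not in the reviewed text and may say more. The finding is limited to the protocol text supplied, where Section 9 sets the sites' reporting duties and is silent.

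**Conclusion.** The point holds and should be fixed, but it does not undermine the trial. For patients who complete treatment, scheduled labs follow 12 of 13 injections, although laboratory results belong to the primary endpoint. The residual gap after existing follow-up is the routine recheck of lower-grade abnormalities, and of non-serious ones not judged probably or definitely related, plus any laboratory effect of the last dose. The pregnancy gap is separate and does not depend on how long the event window is: the supplied text requires no report, no outcome and no congenital-anomaly criterion.

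Whether 7 days (3 to 11) is too short is a judgement that the documents cannot settle, since they give no half-life and no rationale. The conclusion on the window is therefore only that it needs a reason, or that the safety claim must be confined to the on-treatment period.

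Assumptions: the 5.1 text governs visit 13 and visit 14, the course is 13 injections as in the synopsis, and no unscheduled labs are counted.

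**What to change.** - **Labs.** Keep the visit 13 draw and add chemistry and hematology at the existing visit 14, in both 5.1 and the 5.2 calendar. All 13 injections are then followed by a lab, and a visit 13 abnormality gets a recheck about 7 days later. Cost: one extra routine panel per patient, at most 20 for the planned 20 subjects, and no extra visit. This serves patients who reach visit 14. No early-termination labs are listed, and the sponsor should say whether any are intended.
- **Pregnancy.** In Section 9, require prompt reporting of any pregnancy to the sponsor with follow-up to outcome, and add congenital anomaly to the 9.2 list. Cost: a few sentences, and follow-up only where a pregnancy occurs.
- **Window.** State why new-event capture ends about 7 days after the last injection, citing the drug's persistence. Otherwise, say in Section 10.5.2 and in the report that the safety conclusion covers the on-treatment period only. Cost: text only.
- **Reconciliation, separately.** Align the calendar with 5.1, 6.1 and the synopsis on the visit 14 injection and PK marks, and on the early lab visits (2 and 4 against 3 and 5).
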